Appendix 1: World Medical Association Declaration of Helsinki-Ethical Principles for Medical Research on Human Patients	22
Appendix 2: Informed Consent Form	29
Appendix 3: Adverse Event Definitions and Safety Reporting for Investigators (as per requirements for marketed products).....	31
a. Definitions	31
b. Classification of Adverse Events	32
c. Clarification in Reporting of Deaths.....	33
d. Causality of the adverse event	33
e. Laboratory Abnormalities	34
f. Documentation of Adverse Events	34
g. Follow-up of Adverse Events and Serious Adverse Events.....	35
h. SAE/SADRs reporting (Investigator’s Responsibilities)	35
i. Infusion Reactions	37
Appendix 4: Package Insert	38

3. Background

Coronavirus disease 2019 (COVID-19) progresses to respiratory complications as consequence of the exaggerated immune response of the host, producing a pro-inflammatory cytokine storm syndrome (i.e.: IL-6, TNF) and cytopenia, with a high mortality rate.

Emergency treatments aiming to reduce individual cytokines (IL-6 and IL-1) specifically [or indirectly (JAK inhibitors and CCR5 antagonists) have shown survival benefit in patients with hyperinflammation, without increased adverse events.

However, not being sufficient to reduce the rising mortality by COVID-19 other interventions to immunomodulate the life-threatening hyperinflammation are urgently needed.

Therefore, the proposal for use of an anti-CD6 monoclonal antibody (Itolizumab) for the treatment of the COVID-19 cytokine storm syndrome complication.

Why CD6?

CD6 is constitutively expressed mainly on effector T cells (Teff) and hardly expressed on regulatory T cells (Tregs). CD6 stimulates the immune response and is overexpressed after lymphocyte activation. CD6 homes inflammatory cells to lesion, and its ligand ALCAM is upregulated after activation and in inflamed tissues.

CD6 and viruses:

CD6 is overexpressed on T-cells during chronic SIV infection, with impaired anti-viral responses, and is associated with SIV disease progression. HTLV-1 induces overexpression of ALCAM facilitating the trafficking of infected lymphocytes through the blood-brain barrier. ALCAM is increased on HIV+ monocytes and anti-ALCAM antibodies and the CCR2/CCR5 dual inhibitor reduce their transmigration.

Why Itolizumab?

Itolizumab is an anti-CD6 humanized IgG1 mAb. Itolizumab is an immune modulatory molecule. Itolizumab accumulates in the inflamed lesion. Itolizumab is used in Psoriasis and evaluated in other inflammatory diseases (Rheumatoid Arthritis) with a good safety profile as monotherapy or in combination with other drugs. Itolizumab has a legacy of therapeutic effect after discontinuation of the treatment period. Itolizumab has a potent anti-inflammatory effect reducing the production of pro-inflammatory cytokines IL-6, TNF, IFN γ , IL-17 and IL-1.

Hypothesis:

Itolizumab in COVID-19 patients will control the pro-inflammatory cytokine storm syndrome, by immunomodulation of Teff function and trafficking to the inflammation site, sparing Tregs and preserving the anti-viral response, reducing the morbidity and mortality.

Summary of Clinical Safety with Itolizumab:

Itolizumab Injection has been administered to 338 patients with RA or psoriasis (including those with psoriatic arthritis) for up to 52 weeks in clinical trials till date and has been found to be well tolerated and safe.

Itolizumab Injection (Alzumab™) was launched in India on 10 Aug 2013, as a solution for IV infusion of 1.6 mg/kg once every two weeks for 12 weeks, followed by 1.6 mg/kg every four weeks up to 24 weeks (each 5 mL vial contains 25 mg of itolizumab) for the treatment of patients with active moderate to severe chronic plaque psoriasis who are candidates for systemic therapy.

Post-marketing, periodic safety update reports (PSURs) have been generated and submitted to the licensing authority. Based on these periodic reviews of safety data, the overall safety profile evaluation for Itolizumab Injection has remained unchanged. No new clinically significant issues arose which warranted changes to the current reference safety information (RSI).

The most commonly (occurring in $\geq 5\%$ patients) reported AEs in the Phase 3 study were infusion reactions (which are managed by premedication), pyrexia, upper respiratory tract infections and pruritus. The majority of the events were mild or moderate in severity. There were small transient reductions observed in the mean ALC during the initial infusions; however ALC increased with continued dosing. The small reduction in ALC did not appear to increase the incidence of infection.

Summary of Contraindications/warning:

ALZUMAB™ should not be administered to patients having history of severe allergy or known hypersensitivity reaction to any component of ALZUMAB™ or any murine proteins. Additionally, ALZUMAB™ is contraindicated in patients with any active serious infection including tuberculosis and HIV-AIDS.

It is recommended that live/attenuated vaccines not be given concurrently with ALZUMAB™.

As with other IgG antibodies, itolizumab may cross the placenta during pregnancy. The available clinical experience is too limited to exclude a risk, and administration of ALZUMAB™ is therefore not recommended during pregnancy.

Infections and Reactivation of Tuberculosis

Physicians should exercise caution before and during Itolizumab Injection treatment in patients with a history of recurrent infections or underlying conditions which may predispose them to serious infections. Patients should be monitored closely for the development of signs and symptoms of infection during and after treatment with Itolizumab.

4. Objectives

Primary Objectives:

To study the efficacy and safety of adding Itolizumab in patients with Moderate to Severe COVID-19 complications (Cytokine Release Syndrome).

Secondary Objectives:

To study the effect of immunomodulation by Itolizumab and its correlation to clinical improvement by evaluating biomarker data (IL6, TNF-a, IL17, IL1, Interferon -A etc.) before and after Itolizumab treatment

5. Outcome Measures

Primary Outcome Measures:

1. Proportion of patients with deterioration of lung function as measured by*:
 - Stable SpO₂ without increasing FiO₂
 - Stable PaO₂ without increasing FiO₂
2. Reduction of endo-tracheal intubation rate, measured as rate of patients needing intubation*
3. Reduction in proportion of patients who need*
 - Non-invasive ventilation
 - Invasive mechanical ventilation
 - High flow nasal oxygen
4. Time of duration of mechanical ventilation or time to end of mechanical, measured as elapsed time from the start date of mechanical ventilation to the weaning date, for patients needing intubation*
5. One-month mortality rate between the two arms* [Time Frame: up to 1 month]

1-month mortality is defined as the ratio of patients who will live after 1month from study start out of those registered at baseline

6. Change in inflammatory markers like CRP (C-reactive protein) level, d-Dimer, ferritin etc. [Time Frame: Arm A; baseline, during treatment (Before every dose and 12 to 24 h after every dose) up to 1 month, Arm B: baseline, 12 to 24 h and approx. 7 and 14 days after randomization]

Secondary Outcome Measures:

1. Biomarkers (IL-6, TNF-a, IL1, IL17, etc...) [Time Frame: Arm A; baseline, during treatment (Before every dose and 12 to 24 h post dose) up to 1 month, Arm B; baseline, 12 to 24 h and approx. 7 and 14 days after randomization]
2. Lymphocyte count [Time Frame: Arm A; baseline and before every dose up to 1 month, Arm B; baseline, approx. 7 and 14 days after randomization]
Lymphocyte count assessed by routinely used determination of blood count
3. PaO₂ (partial pressure of oxygen) / FiO₂ (fraction of inspired oxygen, FiO₂) ratio (or P/F ratio) [Time Frame: Arm A; baseline, during treatment (Before every dose and 48 h post dose) up to 1 month, Arm B: baseline, 48 h and approx. 7 and 14 days after randomization]
calculated from arterial blood gas analyses (values from 300 to 100)
4. Number of participants with treatment-related side effects as assessed by Common Terminology Criteria for Adverse Event (CTCAE) version 5.0 [Time Frame: during treatment and up to 30 days after the last treatment dose]*
graded according to CTCAE criteria (v5.0)
5. Radiological response [Time Frame: at baseline, after seven days and if clinically indicated (up to 1 month)]*
Thoracic CT scan or Chest XR
6. Duration of hospitalization [Time Frame: from baseline up to patient's discharge (up to 1 month)]*
Days of hospitalization and ICU
7. Remission of respiratory symptoms [Time Frame: up to 1 month]*
time to independence from non-invasive mechanical ventilation calculated in days
8. Remission of respiratory symptoms [Time Frame: up to 1 month]*
time to independence from oxygen therapy in days

* Applicable for both arms

6. Population

Patients who have tested positive for virological diagnosis of SARS-CoV2 infection (PCR) are planned to be randomised for enrolment from various centres in India.

Inclusion Criteria:

1. Male or female adults above 18 years (not tested in children yet)
2. Informed consent for participation in the study
3. Confirmed virological diagnosis of SARS-CoV2 infection (RT-PCR)
4. Hospitalized due to clinical worsening of COVID-19 infection
5. Oxygen saturation at rest in ambient air $\leq 94\%$
6. Patients who are in moderate to severe ARDS as defined by PaO₂/Fio₂ ratio of < 200 or more than 25% deterioration from the immediate previous value.
7. Baseline serum ferritin level ≥ 400 ng/mL or IL-6 levels greater than 4 times ULN, if known

Note: Either of Inclusion number 6 or 7 is required for inclusion of the patient into the study. Since there is logistical delay in getting results in time, biomarker data as inclusion criteria may be used if already known.

Exclusion Criteria:

1. Known severe allergic reactions to monoclonal antibodies
2. Active tuberculosis (TB) infection
3. History of inadequately treated tuberculosis or latent tuberculosis

Note: Latent tuberculosis should be excluded based on history, physical examination and chest x ray before dosing (day 1). QuantiFERON TB also should be performed, however considering criticality of patient condition, patient can be dosed without QuantiFERON TB test results. If QuantiFERON TB test is positive, then continuation of patient in the study is investigator's discretion considering benefit-risk evaluation with the sponsor.

4. In the opinion of the investigator, progression to death is highly probable, irrespective of the provision of treatments
5. Patient on invasive mechanical ventilator support.

6. Have received oral anti-rejection or immune-suppressive drugs within the past 6 months

Note: Patient receiving oral anti-rejection or immune-suppressive drugs regularly in the last 6 months will be excluded. Patient will be included if received short course of steroids.

7. Participating in other drug clinical trials like using anti-IL-6 therapy like tocilizumab (participation in COVID-19 anti-viral trials may be permitted if approved by Sponsor)
8. Patient on treatment of anti-IL-6 or plasma therapy as a part of supportive care

9. Pregnant or breastfeeding, or positive pregnancy test in a pre-dose examination
10. Any serious medical condition or abnormality of clinical laboratory tests that, in the investigator's judgment, precludes the patient's safe participation in and completion of the study
11. Patients with known history of Hepatitis B, Hepatitis C or HIV
12. Absolute Neutrophils count (ANC) $<1000 / \text{mm}^3$
13. Platelet count $<50,000 / \text{mm}^3$
14. Absolute Lymphocyte count (ALC): $<500/\text{mm}^3$

Note: ANC, ALC and platelet counts can be done in local lab in the hospital.

Planned number of subjects:

Approximately 30 patients are considered sufficient to explore the study objectives and will be included in this study (number of patients may be increased if there is benefit observed in initial cohort of patients. There is no formal sample size calculation estimated).

Method of assigning patient to treatment group:

All eligible patients entering into the study will be randomized in 2:1 ratio to receive the treatment A/ B respectively. A computer derived randomization schedule is planned to be generated using appropriate system e.g. SAS to assign patient to treatment groups. Randomization will be central and appropriate system (e.g. remote telephone based, computer-based email, sealed envelope) will be used to distribute randomization schedule to the site

Note: If the patient is randomised to Arm A and is not initiated itolizumab or not administer one full infusion, is then not considered randomized. The same randomisation code will be used for the subsequent subject in that particular site.

Approximate number of sites:

1-10 sites

7. Treatment

Treatment Intervention and Dose:

Arm A: Best supportive care + Itolizumab

The best supportive care to be given as per the institutions protocol will be administered

(e.g: antivirals /antibiotics/ hydroxychloroquine; oxygen therapy, etc) + **Itolizumab**

Itolizumab

Note: Premedication: Hydrocortisone 100 mg i.v (or equivalent short acting glucocorticoid) and Pheniramine 30 mg per i.v. about 30 ± 10 minutes prior to infusion.

Start at 1.6 mg/kg dose iv infusion, if well tolerated, investigator has the discretion to continue with 1.6 mg/kg dose every 2 weeks or 0.8 mg/kg weekly regimen.

Subsequent dose and frequency can be modified, deferred or stopped if patient recovers as per investigator's discretion. If patients' overall parameters improve (if performed and RT-PCR is negative) further dose need not be given. Total infusion received during study duration can vary from 1 to 4 for each patient.

Arm B: Best supportive care

The best supportive care to be given as per the institutions protocol will be administered

(e.g: antivirals/antibiotics/ hydroxychloroquine; oxygen therapy, etc)

Dosing, Handling and Storage of Itolizumab

- Itolizumab is to be stored in 6R, USP type-1, 10 mL glass vials, refrigerated condition at 2°C to 8°C and is stable at that temperature for 36 months.
- Itolizumab is intended for use under the guidance and supervision of a physician. The diluted infusion solution should be prepared by a trained medical professional using aseptic technique; as follows:
- Calculate the dose and number of itolizumab vials needed. Itolizumab is provided as preservative-free single-use vial for IV infusion. Each vial contains 25 mg of itolizumab (5 mg/mL) in a sterile, clear, colourless, preservative-free buffer
- Itolizumab should be administered via IV infusion in 250 mL of 0.9% Sodium Chloride solution (normal saline). For this, dilute the appropriate dose of itolizumab to 250 mL with sterile normal saline. Gently mix. The total volume of the infusion will be more than 250 ml due to addition of the drug solution to 250 mL of 0.9% Sodium Chloride solution.
- Fully diluted itolizumab solution should be allowed to reach room temperature prior to infusion. Before use, the fully diluted itolizumab solution may be stored at room temperature or refrigerated at 2-8°C (36°F-46°F) protected from light. Itolizumab is stable in an infusion bag containing 250 mL of normal saline for up to 10 hours at room temperature. Do not administer as IV push or bolus.
- The infusion must be administered over a period of not less than 120 minutes and using an infusion set with an in-line, sterile, non-pyrogenic, low protein-binding filter (pore size of

1.2 µm or less). Approximately 50 mL of diluted itolizumab solution should be administered during the first hour, followed by remaining solution (more than approximately 200 mL) in the next hour. The infusion period can be extended up to 8 hours for medical reasons.

- The vials do not contain antibacterial preservatives. Therefore, any unused portion of the solution should not be stored for reuse.

Study Drug Discontinuation:

The investigator may decide to terminate the participation and discontinue further study participation of any patient. The recommended withdrawal criteria and dosing interruption criteria are presented below:

1. Protocol violation: If a protocol violation occurs that in the clinical judgment of the investigator and/or after discussion with the sponsor may invalidate the trial, the patient will be withdrawn by the investigator.
2. Consent is withdrawn: Patients have the right to withdraw from the trial at any time for any reason.
3. Serious, life-threatening, or intolerable AEs or laboratory abnormalities in the investigator's opinion, requires withdrawal from the study for safety reasons.
4. Need arises to treat the patient with any medication that is not allowed as concomitant medication during the study; use of which, in the opinion of the investigator and/or medical monitor invalidates the study results or compromises the patient safety if continued on the study drug.
5. The investigator also withdraws a patient if the sponsor terminates the study.

8. Assessments

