8.1 Schedule of Study Visits and Procedures

Visit	S1	W1	W2	W3	W4	End of Study
Weeks	-2 to 0	0	1	2	3	4 th week
Days	-14	1 [^]	8 [^]	15 [^]	22 [^]	30 [#]
Event						
Informed Consent	X					
Medical History	X					
Inclusion/Exclusion Criteria ^a	X					
Weight	X	X	X	X	X	X
Physical Examination, Vital signs ^{\$}	X	X	X	X	X	X
Hematology* [;] ^{\$}	X	X	X	X	X	X
Biochemistry** [;] ^{\$}	X	X	X	X	X	X
Chest X Ray/CT scan ##	X	X	X	X	X	
Randomisation	X					
Best Supportive Care		X	X	X	X	
Pre-medication @ in Arm A		X	X	X	X	
ALZUMAb infusion ^b		X	X	X	X	
Cytokines and Immunophenotyping assessment	X	X ^d				
PaO ₂ /FiO ₂ ratio	X	X	X	X	X	
CRP	X	X	X	X	X	X
Daily Morning SOFA Score ^c	X	X	X	X	X	
Concomitant medication check	X	X	X	X	X	X
Adverse events	X	X	X	X	X	X

[^] Window period: ± 48 Hours.

^a All inclusion / Exclusion criteria to be reviewed prior to first dosing. Screening period is up to 14 days however screening and baseline visit can happen in one day and screening assessment can be considered as baseline assessments.

^b 1.6 mg/kg dose iv infusion, if well tolerated and improvement in patient observed, investigator has the discretion to continue with 1.6 mg/kg dose every 2 weeks or 0.8 mg/kg weekly regimen in combination therapy with standard of care (anti-viral and antibiotic drugs). Subsequent dose and frequency can be modified, deferred or stopped if patient recovers as per investigator's

discretion. If patients' overall parameters improve (if performed and RT-PCR is negative) further dose need not be given. Total infusion received during study duration can vary from 1 to 4 for each patient. If patient recovers/is discharged earlier than 30 days, then patient should be contacted telephonically to get status of the patient on 30th day after enrolment.

c: Daily SOFA Scoring until patient moved out of ICU/equivalent, and later SOFA score frequency as per investigator discretion. If patient is not admitted in the ICU/equivalent at the time of enrolment, then it is recommended to capture these assessments daily for first 7 days.

Window period for assessment at 4th week or 30th day is \pm 3 days.

*Hematology assessments (blood test) include: hemoglobin, total leukocyte count, differential count, absolute neutrophil count, absolute lymphocyte count, and platelet count.

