For the evaluation of safety, all the evidences of adverse events occurring during the study will be considered. The clinical laboratory tests will be conducted at local labs as and when necessary for safety evaluation. Any investigation, at any time during the study may be conducted at the local lab as per investigator's discretion, in order to monitor safety. Definitions of adverse events and safety reporting for SAEs and SUSARs will be as per regulatory requirements for marketed products (Refer Appendix 3 for details on definitions and reporting that Investigators must follow to satisfy regulatory requirements and ensure patient safety and well-being).

Special Precautions

In general, according to previous data, ALZUMAbTM is safe and well tolerated. However, it is recommended that investigators should exercise caution before administering ALZUMAbTM in subjects with a history of recurrent infections, or underlying conditions which may predispose them to infections. Subjects who develop a new infection while undergoing treatment with ALZUMAbTM should be monitored closely and treated according to standard treatment guidelines. While previous clinical study data has not revealed the incidence of opportunistic infections, it is recommended that Investigators be watchful for occurrence of tuberculosis and opportunistic infections like candidiasis. Administration of ALZUMAbTM should be discontinued if a subject develops a serious infection (other than COVID19). In case a reactivation of latent tuberculosis occurs in study subjects during the clinical study, immediate treatment in accordance with standard medical practice should be instituted and the subjects should be withdrawn from the study.

10.Data Handling Procedures

Source Documents

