The SAE will not be closed out if it is of changing severity during the course. It will be reported with changes in the severity as it upgrades in follow up reports such that each upgraded sequelae will not be recorded as a new SAE but continuation of same SAE and the serious and unexpected adverse

reactions will be reported to DCGI within the stipulated timeline. Only the highest grade of severity will be considered for analysis purpose.

c. Clarification in Reporting of Deaths

All subject deaths (regardless of relationship to study drug) should be reported for subjects while on the study protocol. This should be recorded on the end of study CRF page and the SAE form. If a subject dies after signing consent but before the first dose of the study drug, this will also be recorded in the CRF. Death is an outcome of an adverse event and not an adverse event in itself. All reports of subject death should include an adverse event term (other than “Death”) for the cause of the death. If an adverse event term is not provided, the treating physician will be queried to obtain the cause of death. Only in the rare occurrence that no verbatim description of an adverse event can be obtained from the investigative site, will “Death-Unknown cause” be used as the event term.

d. Causality of the adverse event:

The Investigator’s causality assessment should consider the potential etiologies for the observed adverse event. An adverse event may be related to the study drug, other concomitant medications, the underlying disease pathology, inter-current illness, a procedure performed in the course of the study, or another reason. Among the potential etiologies, the investigator should make a determination based on the most likely causal relationship. When a causality assessment is provided for a SAE, it is important to include a rationale for the assessment so that a better understanding of the reported event can be compiled. The rationale should be accompanied by all available supporting evidence, including relevant laboratory tests, histopathology evaluations and the results of other diagnostic procedures.

The Investigator will make a judgment considering whether or not, in his opinion, the adverse event was related to the drug according to the following classification.

The likelihood of the relationship of the adverse event to the study drug is to be recorded as follows.

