Subjects will be monitored for adverse events/reactions to the study drug and/or study procedures during the study product administration. All AEs related to ALZUMAbTM and all SAEs must be followed until resolution, until the condition stabilizes, until the event is otherwise explained, or until the subject dies or is lost to follow-up. The investigator will administer appropriate treatment for the SAE resolution. The Investigator is responsible to ensure that follow-up includes any supplemental investigations as may be indicated to elucidate as completely as practical the nature and/or causality of the AE/SAE. This may include additional laboratory tests or investigations, histopathological examinations, or consultation with other health care professionals.

h. SAE/SADRs reporting (Investigator's Responsibilities)

All study drug related SAEs (SADRs), occurring **after the patient signs the informed consent and until the one year follow-up period is over or until the patient has prematurely stopped participation in the study** must be reported to drug manufacturer (Biocon Ltd) within 24 hours of learning of its occurrence.

Recurrent episodes, complications, or progression of the initial SADRs must be reported as follow-up to the original episode within 24 hours of the Investigator receiving the follow-up information. An SADR occurring at a different time interval should be reported separately as a new event.

Information about all SADRs is collected and recorded on the Serious Adverse Event Report Form. The Investigator must assess the relationship to drug and report all SADRs by completing the SAE Report Form in English, and send the completed, signed form within 24 hours to Biocon Ltd. The original SAE Report Form and the fax confirmation sheet must be kept with the documentation at the site. The investigator should notify all SADRs to Biocon through email. The telephone and fax number of the contact persons listed below for SADRs reporting can be used as alternate modes of communication.

The Investigator must **inform one of the responsible persons** of Biocon Ltd (Pharmacovigilance personnel listed below) **by telephone as soon as possible and not later than 24 hours** of the occurrence of an SADR.

Questions pertaining to a specific serious adverse drug reaction occurring in a patient should be directed to the contact persons listed in the protocol.

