### 14.3.4 Treatment Emergent Adverse Event (TEAE) related to study drug

System Organ Class	Preferred term	ARM A (N=XX) [n (%)]		ARM B (N=XX) [n (%)]	
		Related	Not related	Related	Not related
Any SOC		XX (XX.X %)	XX (XX.X %)	XX (XX.X %)	XX (XX.X %)
	PT1	XX (XX.X %)	XX (XX.X %)	XX (XX.X %)	XX (XX.X %)
	PT2	XX (XX.X %)	XX (XX.X %)	XX (XX.X %)	XX (XX.X %)
SOC1		XX (XX.X %)	XX (XX.X %)	XX (XX.X %)	XX (XX.X %)
	PT1	XX (XX.X %)	XX (XX.X %)	XX (XX.X %)	XX (XX.X %)
	PT2	XX (XX.X %)	XX (XX.X %)	XX (XX.X %)	XX (XX.X %)
	PT3	XX (XX.X %)	XX (XX.X %)	XX (XX.X %)	XX (XX.X %)

Note: System Organ Class and Preferred Term coded as per MedDRA version XX

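### The only named adverse-event outcome counts drug-related events on a last-dose clock and cannot compare safety between arms; the all-cause tables that could do so lack an Arm B start and a between-arm difference

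*Protocol*

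**What the plan says.** Protocol Section 4 puts efficacy and safety together in the primary objective. In Section 5 the one outcome built on adverse events is secondary outcome 4: "Number of participants with treatment-related side effects as assessed by Common Terminology Criteria for Adverse Event (CTCAE) version 5.0". Its time frame is "during treatment and up to 30 days after the last treatment dose", and its asterisk stands for "Applicable for both arms". SAP 3.2.2 repeats it, and SAP 9 summarises it by frequency and proportion.

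**Causality.** Appendix 3 d states: "The likelihood of the relationship of the adverse event to the study drug is to be recorded as follows". Section 7 gives Arm B supportive care only. SAP shell 14.3.4, "Treatment Emergent Adverse Event (TEAE) related to study drug", still has Related and Not related columns for both arms.

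**Collection.** The schedule in Section 8.1 marks adverse events at screening, at the four weekly visits and at End of Study, without restriction by arm. Section 9 says that "all the evidences of adverse events occurring during the study will be considered", and Appendix 3 f requires every event to go on the CRF. Appendix 3 g says: "Subjects will be monitored for adverse events/reactions to the study drug and/or study procedures during the study product administration". If a patient recovers or is discharged before 30 days, footnote b of Section 8.1 says "then patient should be contacted telephonically to get status of the patient on 30th day after enrolment".

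**Analysis.** SAP shells 14.3.1, 14.3.2, 14.3.3 and 14.3.5 tabulate treatment-emergent events (TEAEs) by arm, whatever their cause. Shells 14.3.1 and 14.3.2 date emergence from the first study-treatment dose. Under SAP 7, Arm B patients enter the safety population by being randomised and Arm A patients by receiving a partial or full dose.

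**The concern.** The trial asks whether adding itolizumab to supportive care is safe. That calls for a comparison of what happens to patients in the two arms. The named outcome instead compares what investigators attribute to a drug that only one arm receives, over a period defined by dosing that only one arm has. It will tend to show some percentage in Arm A against nothing in Arm B, whatever the drug does to overall event rates. It can err in either direction: events attributed to the drug can look like an excess when all-cause rates are equal, and under-attribution in an open-label trial can hide a real excess.

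The all-cause tables are the natural remedy, but they are not the named outcome. They also have three gaps that affect a comparison: no Arm B start for treatment emergence, no between-arm difference or interval, and no stated adverse-event enquiry in the call after early discharge.

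**Working it through.** The documents give no power, effect size or expected event rate, so there is no planned figure to reproduce. The check is mostly a reading of the text, with some side arithmetic.

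**1. Arm sizes.** About 30 patients at 2:1 (Protocol Section 6): 30 × 2/3 = 20 in Arm A and 30 × 1/3 = 10 in Arm B.

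**2. Outcome window.** Nominal infusion days are 1, 8, 15 and 22, and End of Study is Day 30 ± 3, so Day 33 at the latest (Section 8.1). Window end = last-dose day + 30.

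| Last dose | Window ends | Days past Day 33 |
|---|---|---|
| Day 1 | Day 31 | none |
| Day 8 | Day 38 | 5 |
| Day 15 | Day 45 | 12 |
| Day 22 | Day 52 | 19 |

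No visit is scheduled after End of Study. Appendix 3 h extends reporting of drug-related *serious* events further, but that is only part of this outcome. Arm B has no last dose, so no window can be computed for it.

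**3. What a zero in Arm B does.** The SAP plans no test on adverse events, so this is an illustration only, using the two-sided Fisher exact test at 20 v 10.
- 7/20 v 0/10: p = (77,520 + 52,200)/2,035,800 = 0.064.
- 8/20 v 0/10: p = (125,970 + 42,345)/5,852,925 = 0.029.

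So 8 related events in Arm A would reach p < 0.05. If the true related rate in Arm A were 20%, 30%, 40% or 50% (assumed), the chance of 8 or more in 20 is 0.03, 0.23, 0.58 or 0.87, even if all-cause rates were identical in the two arms.

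**4. Events missed after discharge.** Assume a constant daily hazard h, equal in both arms, with capture ending at discharge after t days. Crude incidence = 1 − exp(−h·t).
- 10 v 14 days, h = 0.02: 0.181/0.244 = 0.74. With h = 0.05: 0.393/0.503 = 0.78.
- 12 v 14 days: 0.87 and 0.90 for the same hazards.

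The lengths of stay, the hazards and the loss of post-discharge events are all assumptions.

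**5. Precision of an all-cause comparison.** Exact Fisher power at 20 v 10, for assumed rates in B v A, is 0.13 for 20% v 40%, 0.15 for 50% v 70%, 0.45 for 30% v 70% and 0.63 for 50% v 90%. With 50% in each arm, the standard error of the difference is √(0.25/20 + 0.25/10) = 0.194, so a 95% interval is about ±1.96 × 0.194 = ±38 percentage points.

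**6. The collection passages side by side.** The schedule, Section 9 and Appendix 3 f cover all events in both arms throughout the study. Appendix 3 g describes monitoring during product administration, and Appendix 3 e counts clinically significant laboratory findings as events when they appear or worsen after study drug. Neither says what applies to an Arm B patient. The broader passages are explicit, so this is a conflict to reconcile and not a limit on collection.

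**The case against.** A reader might infer that adverse-event monitoring as a whole is tied to drug administration and that the plan offers no fair safety comparison. The documents do not support that. Adverse events are marked at every visit without restriction by arm, although premedication in the same table is restricted to Arm A. Every event must be documented, and all deaths are reported regardless of relationship. The Appendix 3 g sentence sits under follow-up of events and does not override these rules. The SAP tabulates any, grade 3 or above, serious and fatal TEAEs by arm. One-month mortality is a primary outcome for which a difference, 95% interval and p-value may be given, and lymphocyte count has an interval for the between-treatment difference. All of this stands.

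It is also fair to say that a zero in Arm B is an inference. The documents do not define relatedness for Arm B, and Listing 16.1.12 files supportive care under study treatment. But the causality scale refers only to the study drug, so zero is the expected result.

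The ratios of 0.74 to 0.90 are not predictions. Adverse events are due at End of Study, and SAP 13 accepts telephone information on oxygen weaning, so the call can carry clinical detail. A bias arises only if stays differ between arms and post-discharge events are missed.

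Finally, a risk difference from 20 v 10 patients will be imprecise. That is true, but it is a reason to show the interval.

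**Conclusion.** The point holds for the named outcome and for three specific gaps in the all-cause analysis. As written, secondary outcome 4 is expected to return zero in Arm B, has no defined window there, depends on open-label attribution in Arm A, and runs 5 to 19 days past the latest End of Study day after a last dose on Days 8 to 22. It cannot serve as a between-arm safety comparison.

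The trial as a whole does plan all-cause safety data by arm. What that analysis lacks is an Arm B start for treatment emergence, a between-arm difference with its interval, and stated adverse-event questions after early discharge. The expected zero rests on reading relatedness as relatedness to itolizumab, as Appendix 3 d does. The Fisher and incidence-ratio figures are illustrations under assumed rates, stays and hazards. The change is worth making because it removes attribution from the comparison and costs little.

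**What to change.** - **Outcome.** In Protocol Section 5 and SAP 3.2.2, make the between-arm safety outcome all-cause: patients with any TEAE, any grade 3 or above TEAE, any SAE and any infection, with risk difference and 95% interval.
- **Window.** Use one common Day 1 to the Day 30 End of Study visit in both arms. Day 1 is first dose in Arm A and a stated matching day, such as randomisation, in Arm B. SAP 8 already pairs first dose with randomisation when it defines baseline. If dosing can follow randomisation by a day or more, state how the two starts are aligned. Give the same Arm B start in the TEAE definition of shells 14.3.1 and 14.3.2.
- **Drug-related events.** Report them descriptively for Arm A only, including any collected after Day 30.
- **Day 30 call.** Add questions on adverse events, infection and readmission.
- **Appendix 3 g.** Keep the sentence on monitoring during administration, and add that adverse events are collected in both arms throughout the study, so that it agrees with Section 8.1, Section 9 and Appendix 3 f.

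The cost is some wording, a few table entries, a few questions in a call already made, and more low-grade events to record. The intervals will be wide with about 30 patients and should be presented as such.
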